7.1.13 Correlative Studies Blood Sampling

Blood samples will be collected pre-dose on Day 1, Week 6, Week 21, and end of ibrutinib therapy for immune testing per Schedule of Events. They will be performed at investigator's discretion if early study termination. For sampling requirements, see Section 7.2.

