7.2 RESEARCH BLOOD SPECIMEN PREPARATION, HANDLING, AND STORAGE

Blood samples for correlative studies will be collected at baseline (prior to first dose of study drug), at week 9, week 12, and end of ibrutinib treatment. Peripheral blood will be utilized with an estimated volume of 50 cc collected in five green top tubes.

1. Preparation of Samples

Whole blood samples in 5 green top tubes (10ml/tube) will be received in the laboratory of [name]. Plasma will be isolated by centrifugation of the green top tubes for 5min at 1500rpm and lymphocyte isolation will be performed using Ficol gradient isolation for the purpose of immune testing.

2. Sample Storage

For storage, plasma will be held in 1.5 ml aliquots and placed in a -20C freezer. Lymphocytes will be frozen using 90% FBS and 10% DMSO and placed in a -80C freezer for short term storage. Long term storage of lymphocytes will be conducted utilizing liquid nitrogen.

3. Long-Term Use of Samples

Any isolated plasma and lymphocytes will be stored for the duration of the trial utilizing the short term method above and will be tested per protocol parameters outlined in Section 4.1. With the subject's permission, any samples remaining at the end of the trial will be placed in long term storage for use in future research. If any subject does not agree, that subject's remaining samples will be destroyed at the final closure of the trial.

4. Procedure for Clinical Trial Staff

The following procedure is recommended to be used for collaboration with the Research Science Lab:

- a. Notify the Research lab at least 2 days prior to the collection, using the template below.
Email to [contact] and cc [contact]
Follow up with a phone message to [name].
- b. Prepare a plastic bag with 5 green top tubes (tubes obtained from [name] lab). Attach label to tubes with MCC #, subject MRN, and date of collection. Each bag will have a label attached with the MCC #, subject MRN, DOB, initials, date/time of collection. Label should have research lab contact information. ("Contact [name] or [contact] for pick-up").
- c. Deliver bag of tubes to the Blood Draw area the day prior to collection.

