7.3.2 ENROLLMENT/BASELINE

7.3.2.1 Baseline Visit (Week 0)

- Verify subject still meets inclusion/exclusion criteria.
- Review results of serum pregnancy test, if applicable.
- History and assessment to include directed physical examination, vital signs, and concomitant medication review. Assess and record baseline symptoms prior to study drug administration.
- ECOG performance status assessment
- CBC with differential
- Chemistry profile (ALT, AST, alkaline phosphatase, total bilirubin, calcium, bicarbonate, sodium, potassium, chloride, creatinine, BUN, total protein and albumin)
- Tumor lysis syndrome evaluation (TLS) using BUN, creatinine, phosphorus, potassium, LDH, uric acid results.
- Blood for correlative studies
- Study drug administration (initiation of pembrolizumab IV).

7.3.2.2 Week 1 and 2

- Serum chemistry profile and TLS evaluation by laboratory tests. TLS evaluation will occur on days 1-3 from initiation of therapy.
- Review of tests and assessment for TLS by the investigator or qualified designee.

7.3.2.3 Week 3

- Directed physical examination, vital signs and brief review of systems.
- Medication reconciliation.
- Toxicity/ AE assessment
- ECOG performance status assessment.
- Hematology (hemoglobin, HCT, RBC, WBC with differential [neutrophils, bands, lymphocytes, monocytes, eosinophils and basophils])
- Chemistry (ALT, AST, alkaline phosphatase, total bilirubin, LDH, calcium, bicarbonate, sodium, potassium, chloride, creatinine, BUN, total protein and albumin)

- TLS evaluation
- Study drug administration (pembrolizumab).

7.3.2.4 Week 6

- Directed physical examination, vital signs and brief review of systems.
- Medication reconciliation.
- Toxicity/ AE assessment
- ECOG performance status assessment.
- Hematology (hemoglobin, HCT, RBC, WBC with differential [neutrophils, bands, lymphocytes, monocytes, eosinophils and basophils])
- Chemistry (ALT, AST, alkaline phosphatase, total bilirubin, LDH, calcium, bicarbonate, sodium, potassium, chloride, creatinine, BUN, total protein and albumin)
- TLS evaluation
- Blood for correlative studies
- Prevnar 13 vaccination
- Study drug administration (pembrolizumab and start of ibrutinib by mouth daily for up to 12 months). Medications may be administered in any order on days of infusions.
- Provide pill diary and instruct subject on the recording of data on diary.

7.3.2.5 Week 7 and 8

- Serum chemistry profile and TLS evaluation by laboratory tests.

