- Review of tests and assessment for TLS by the investigator or qualified designee.

7.3.2.6 Week 9

- Directed physical examination, vital signs and brief review of systems.
- Medication reconciliation.
- Toxicity/ AE assessment
- ECOG performance status assessment.
- Hematology (hemoglobin, HCT, RBC, WBC with differential [neutrophils, bands, lymphocytes, monocytes, eosinophils and basophils])
- Chemistry (ALT, AST, alkaline phosphatase, total bilirubin, LDH, calcium, bicarbonate, sodium, potassium, chloride, creatinine, BUN, total protein and albumin)
- Study drug administration (pembrolizumab and ibrutinib).

- Provide pill diary
- Serum chemistry profile and TLS evaluation by laboratory tests.
- Review of tests and assessment for TLS by the investigator or qualified designee.

7.3.2.7 Week 10

- Serum chemistry profile and TLS evaluation by laboratory tests.
- Review of tests and assessment for TLS by the investigator or qualified designee.

7.3.2.8 Weeks 12, 15, 18, 21

- Directed physical examination, vital signs and brief review of systems.
- Medication reconciliation.
- Toxicity/ AE assessment
- ECOG performance status assessment.
- Hematology (hemoglobin, HCT, RBC, WBC with differential [neutrophils, bands, lymphocytes, monocytes, eosinophils and basophils])
- Chemistry (ALT, AST, alkaline phosphatase, total bilirubin, LDH, calcium, bicarbonate, sodium, potassium, chloride, creatinine, BUN, total protein and albumin)
- Study drug administration (ibrutinib and pembrolizumab).
- CT scan week 12.
- Blood for correlative studies week 21
- Provide pill diary.

7.3.2.9 Week 24

- Directed physical examination, vital signs and brief review of systems.
- Medication reconciliation.
- Toxicity/ AE assessment
- ECOG performance status assessment.
- Hematology (hemoglobin, HCT, RBC, WBC with differential [neutrophils, bands, lymphocytes, monocytes, eosinophils and basophils])
- Chemistry (ALT, AST, alkaline phosphatase, total bilirubin, LDH, calcium, bicarbonate, sodium, potassium, chloride, creatinine, BUN, total protein and albumin)
- Tumor imaging (CT scans).

- Study drug administration (ibrutinib and pembrolizumab).
- Provide pill diary

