¹⁰ Tumor imaging will consist of CT of the neck, chest, abdomen and pelvis that will be performed at screening, if not done within 3 months prior to study entry. Response assessment will be done at week 12, week 24, and end of 51 weeks of treatment. CT scans may be performed at different intervals at investigator discretion (i.e. suspicion of progressive disease). Imaging studies post treatment discontinuation will be performed per investigator discretion (including end of treatment imaging assessment).

¹¹ Bone marrow biopsy will be performed at screening (if not performed within 30 days) and after the end of pembrolizumab and ibrutinib therapy (28-35 days after week 51). If subject discontinues treatment early or progression of disease is suspected, a bone marrow biopsy will be per investigator discretion. During follow-up, bone marrow biopsies will be performed per investigator discretion.

¹² Correlative studies. Please refer to Section 4.1 for biomarkers to be studied. They will be performed at baseline (prior to first dose of study drug), at week 6, week 21, and end of ibrutinib treatment. See Section 7.2 for correlative sample collection procedure. They will be performed at investigator's discretion if early study termination

¹³ Safety follow-up will be 90 days after the end of pembrolizumab treatment (may be at the regularly scheduled monthly visit that is nearest to 90 days if continuing on ibrutinib treatment) and 30 days post discontinuation of ibrutinib treatment. If the subject discontinues early, safety follow up must occur before first dose of the next therapy.

¹⁴ Follow-up after a subject has discontinued trial treatment will be every 12 weeks for 12 months.

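### Section 7.2 puts the two middle correlative blood draws at weeks 9 and 12, while every other schedule in the protocol says weeks 6 and 21; following 7.2 would lose the draw taken before ibrutinib and the vaccine.

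*Combined protocol and SAP*

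**What the plan says.** Section 7.2, on research blood specimens, places correlative blood at baseline and then "at week 9, week 12, and end of ibrutinib treatment".

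The other places that set these draws are:

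- Section 7.1.13: "Blood samples will be collected pre-dose on Day 1, Week 6, Week 21, and end of ibrutinib therapy". It ties this timing to the Schedule of Events and closes with "For sampling requirements, see Section 7.2".
- Footnote 12 of the Schedule of Events (7.3.7): "They will be performed at baseline (prior to first dose of study drug), at week 6, week 21, and end of ibrutinib treatment". It then adds "See Section 7.2 for correlative sample collection procedure".
- Visit lists: 7.3.2.1 (week 0) and 7.3.2.4 (week 6) each carry the item "Blood for correlative studies". Section 7.3.2.8, which covers weeks 12 to 21, carries "Blood for correlative studies week 21". The week 9 list (7.3.2.6) has no correlative draw.
- The correlative row of the Schedule of Events, counted by column, is marked at weeks 0, 6, 21 and end of treatment.

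Week 6 is also the visit at which treatment changes. Its list includes "Study drug administration (pembrolizumab and start of ibrutinib by mouth daily for up to 12 months" and the Prevnar 13 injection, which Section 7.7 likewise places on day 1 of week 6. Section 10.2.4 plans its correlative analyses around four time points.

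**The concern.** A blood draw missed at its visit cannot be replaced later. Under the majority schedule, the week 6 draw is the only one taken after pembrolizumab has started but before ibrutinib and the vaccine. Under 7.2, both middle draws come after all three. The section with the odd weeks is also the one that tells staff when to notify the laboratory, which tubes to prepare and when to deliver them, so it is a text that staff will have in hand when arranging a draw.

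Two parts of the analysis depend on these dates. Section 10.2.4 compares responders with non-responders at each time point, tests changes between time points, and fits mixed models over all four. Sections 4.1 and 10.1 call the immune response to pneumococcal vaccination a secondary endpoint, and the choice of weeks decides how soon after vaccination blood is taken.

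**Working it through.** The plan has no figure of its own to reproduce here. The check compares the schedules and counts weeks and doses.

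**Schedules side by side**

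| Place | Draws |
|---|---|
| 7.2 | baseline, week 9, week 12, end of ibrutinib |
| 7.1.13 | day 1, week 6, week 21, end of ibrutinib (pre-dose) |
| Visit lists 7.3.2.1, 7.3.2.4, 7.3.2.8, 7.3.2.11 | week 0, week 6, week 21, end of treatment |
| 7.3.7, table row | week 0, week 6, week 21, end of treatment |
| 7.3.7, footnote 12 | baseline, week 6, week 21, end of ibrutinib |

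The first and last draws agree and the middle two do not. Both schedules have four draws, so the four time points in 10.2.4 do not settle the matter. The conflict is in running text, and the table row only confirms it.

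**Inputs.** Pembrolizumab every 3 weeks from week 0 (6.1.5, 7.3.2.1). Ibrutinib from week 6 (4.1, 7.3.2.4). Prevnar 13 at week 6 (7.3.2.4, 7.7). Draws before that day's dose (7.1.13). No dose delays assumed.

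**Formulas.** For a draw at week w:

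- weeks on ibrutinib = w − 6
- weeks since vaccine = w − 6
- earlier pembrolizumab doses = w / 3 (doses at weeks 0, 3, …, w − 3)

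| Draw | Schedule | Earlier pembrolizumab doses | Weeks on ibrutinib and since vaccine |
|---|---|---|---|
| Second | majority, week 6 | 6/3 = 2 | 6 − 6 = 0 |
| Second | 7.2, week 9 | 9/3 = 3 | 9 − 6 = 3 |
| Third | majority, week 21 | 21/3 = 7 | 21 − 6 = 15 |
| Third | 7.2, week 12 | 12/3 = 4 | 12 − 6 = 6 |

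**What follows**

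- Draws after pembrolizumab and before ibrutinib: 1 of 4 under the majority schedule, 0 of 4 under 7.2.
- Last draw before the vaccine: the same visit (week 6) under the majority schedule. Under 7.2 it is week 0, six weeks earlier and before any pembrolizumab.
- First draw after the vaccine: 15 weeks later under the majority schedule, 3 weeks later under 7.2.
- Draws in conflict: 2 per patient, so at most 25 × 2 = 50 of 25 × 4 = 100 with full accrual. If the trial stops after the 16 first-stage patients (10.2.1), at most 16 × 2 = 32 of 16 × 4 = 64.

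**The case against.** The strongest reply is that the timing is already settled. Section 7.1.13 states its own weeks and ties them to the Schedule of Events, and Section 7.1.1 makes that schedule the summary of what is done at each visit. Footnote 12 also states its weeks and refers to 7.2 only for the collection procedure. This stands in part: a reader might infer that the protocol gives no hint of which schedule prevails, and that would be too strong. It does not remove the error. Section 7.1.13 refers to 7.2 for sampling requirements in general, and 7.2 gives different weeks as a plain instruction.

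Two other strong readings are tempting. One is that a planned analysis of pembrolizumab alone would be lost. No listed objective, endpoint or analysis names that contrast, the hypotheses concern the combination, and Section 4.1 explains the lead-in by overlapping toxicity. The paired tests in 10.2.4 would allow a week 6 comparison but do not specify one. The other is that patients would be split across six time points. This is a single-centre trial with one research laboratory, and nothing in the documents suggests that different patients would follow different sections.

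Weeks 9 and 12 might also have had a purpose. At 3 and 6 weeks after Prevnar 13 they sit closer to the vaccine than week 21 does. The documents do not say so, but they do not rule it out. This is a fair reason to ask the sponsor.

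**Conclusion.** Section 7.2 is wrong as written: it contradicts all the other places that set these draws. If its weeks were followed, two of four draws per patient would come at the wrong visits, and the pre-dose week 6 sample would be lost for good.

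The reach is moderate. The correlative analyses in 10.2.4 are affected; that section calls them exploratory and gives them no power calculation. A reader might infer that nothing beyond these is touched. That is too narrow, because Sections 4.1 and 10.1 give vaccine response secondary status, although the list in 4.2.2 does not name it and Section 3 puts pneumococcal titers among the exploratory objectives. Complete response, the stopping rules and the paired tests from baseline to week 52 in 10.2.2 do not use the middle draws and are unaffected.

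Three assumptions carry this. Doses run on schedule. The pre-dose instruction in 7.1.13 covers week 6 as well as day 1, since the week 6 list does not itself fix the order of draw, vaccine and first ibrutinib dose. Post-vaccine immune measurements come from the correlative draws, since no separate draw for them is scheduled. The counts of 50 and 32 are ceilings, reached only if 7.2 is followed for every patient.

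**What to change.** In Section 7.2, replace weeks 9 and 12 with week 6 (pre-dose, before Prevnar 13 and the first ibrutinib dose) and week 21, to match the Schedule of Events. Label any sample already drawn at week 9 or 12 with its actual week, and do not pool it with week 6 or week 21 samples.

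The change has one downside. With weeks 6 and 21, the first correlative sample after vaccination comes 15 weeks after Prevnar 13. The sponsor should confirm that this interval is intended for the vaccine-response endpoint. If an earlier post-vaccine sample is wanted, it should be added openly as a further draw in all the places listed above, and the four time points in 10.2.4 revised to match.

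The correction is one sentence by amendment. Sample size, stopping rules, the primary endpoint and the paired secondary tests do not change.

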10.2.2 ANALYSIS OF THE SECONDARY ENDPOINT(S)

1. Change in T cell exhaustion and/or inhibition following treatment
2. Change in serum immunoglobulin levels following treatment
3. Progression free survival (PFS) and association with immune biomarkers

To determine if T cell exhaustion or inhibition have change due to treatment with the combination therapy at baseline immune testing to immune testing following completion of pembrolizumab and ibrutinib treatments (week 52) using paired t-tests with the null hypothesis being that there is no change in immune measurements following treatment (i.e., $H_0: \mu_d = 0$). If the assumptions of normality do not hold upon assessment, we will instead use nonparametric t-tests (i.e., Wilcoxon Sign Rank Test). Similar tests will be used to determine if changes in serum immunoglobulin levels also resulted following treatment. Tests will be one-sided as based on biology expect the change in immune response to be in one direction following treatment. Tests will be considered statistically significant if the p-value is less than 0.05. Assuming the study go on to stage II and enroll 25 patients, we will be able to detect a modest effect size of 0.60. To determine the association of progression free survival (PFS) with immune biomarkers (T cell exhaustion and/or inhibition, serum immunoglobulin levels), Cox proportional hazards models will be fit with assumption of proportional hazards (PH) assumption check via Schoenfeld residuals. If the PH assumption does not hold, we will rely on use of non-parametric methods (Kaplan-Meier curve with log-rank tests) where the biomarkers will be dichotomized for analysis based on an optimal cut-point determination based on an outcome-oriented approach outlined by Contral and O'Quigley (Contal C, O'Quigley J. An application of changepoint methods in studying the effect of age on survival in breast cancer. Computational Statistics & Data Analysis. 1999;30:253-70.). A Cox regression of the log hazard ratio on the continuous biomarker (assuming a standard deviation of 1 and an anticipated event rate of 0.50) will have 80% power at a 0.05 significance level to detect a regression coefficient equal to 0.79 (i.e., hazard ratio of 2.20).

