13.4 PARTICIPANT AND DATA CONFIDENTIALITY

Participant confidentiality is strictly held in trust by the participating investigators, their staff, and the

sponsor and their agents. This confidentiality is extended to cover testing of biological samples and genetic tests in addition to the clinical information relating to participants. Therefore, the study protocol, documentation, data, and all other information generated will be held in strict confidence. No information concerning the study or the data will be released to any unauthorized third party without prior written approval of the sponsor.

The Moffitt study monitor, other authorized representatives of Moffitt, representatives of the IRB or pharmaceutical companies supplying study products may inspect all documents and records required to be maintained by the investigator, including but not limited to, medical records (office, clinic, or hospital) and pharmacy records for the participants in this study. The clinical study site will permit access to such records.

The study participant's contact information will be securely stored at each clinical site for internal use during the study. At the end of the study, all records will continue to be kept in a secure location for as long a period as dictated by local IRB and Institutional regulations.

Study participant research data, which is for purposes of statistical analysis and scientific reporting, will be transmitted to and stored at Moffitt. This will not include the participants' contact or identifying information. Rather, individual participants and their research data will be identified by a unique study identification number. The study data entry and study management systems used by clinical sites and by Moffitt research staff will be secured and password protected. At the end of the study, all study databases will be de-identified and archived at the Moffitt.

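### Section 7.2 sends tubes bearing the record number and draw date to the immune-testing laboratory, and the plan specifies neither coded aliquots nor masked reading

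*Combined protocol and SAP*

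**What the plan says.** Section 7.2 sets out the handling of the correlative blood samples. On the tubes: "Attach label to tubes with MCC #, subject MRN, and date of collection". On the bag that holds them: "Each bag will have a label attached with the MCC #, subject MRN, DOB, initials, date/time of collection". On destination: "Whole blood samples in 5 green top tubes (10ml/tube) will be received in the laboratory of" (the name is removed from the public copy). That laboratory separates plasma and lymphocytes for immune testing. The labelling steps are introduced with "The following procedure is recommended to be used for collaboration with the Research Science Lab".

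The material is stored before testing: "For storage, plasma will be held in 1.5 ml aliquots and placed in a -20C freezer", and lymphocytes are frozen as well. Section 7.2 does not say what is written on these aliquots. No section describes re-coding them or masking the people who run or gate the assays.

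Section 13.4 covers data: "Study participant research data, which is for purposes of statistical analysis and scientific reporting, will be transmitted to and stored at Moffitt". It says these data carry no identifying information and that "individual participants and their research data will be identified by a unique study identification number". It extends confidentiality to the testing of samples but does not mention specimen labels. Section 13.5 describes samples kept after the study as de-identified, yet has them identified by initials and collection date.

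The readings are used in two places. Section 10.2.2 compares exhaustion markers and immunoglobulins before and after treatment at the 0.05 level, and states: "Tests will be one-sided as based on biology expect the change in immune response to be in one direction following treatment". Section 10.2.4 compares responders with non-responders at each of four time points, as exploratory work.

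**The concern.** The trial is open-label with a single arm (Section 4.1), so the change from baseline in a marker is the whole of the evidence that the marker moved. There is no control group in which a directional drift in reading would also appear and cancel. Flow-cytometry gating can involve judgement, and the one-sided test points in the direction the investigators expect. A reader who knows which sample is baseline could therefore move the result without intending to, and the analysis could not tell that movement from a drug effect.

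Decreased T-cell exhaustion is one of the two components of the secondary endpoint on restoration of immune response. Masking the reader is one of the few protections against this bias open to a single-arm trial, and the plan as written leaves it out.

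A separate matter is that Sections 7.2, 13.4 and 13.5 describe three ways of identifying the same patients and samples, and these do not fit together.

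**Working it through.** **What the laboratory can know from the labels**

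| Item | Identification | Source |
|---|---|---|
| Tube | MCC #, record number, collection date | 7.2 |
| Outer bag | MCC #, record number, birth date, initials, collection date and time | 7.2 |
| Frozen aliquot | not stated | 7.2 |
| Research data for analysis | unique study number | 13.4 |
| Sample stored after the study | initials and collection date | 13.5 |

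The MCC # is probably the protocol number, since Section 5.3 uses MCC16622 for another trial. If so, neither label carries a coded subject number.

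The label shows a date and not a study week. But each patient has four draws, they share a record number, and sorting them by date puts baseline first and end of treatment last. The laboratory is also notified at least two days before each collection (7.2). Time point can therefore be recovered from what the laboratory receives, unless a coding step intervenes. Response status cannot be read from the label. It would need access to clinical records, which the documents neither grant nor exclude.

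**What a reading shift would do to the planned test (illustration)**

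Inputs from 10.2.2: n = 25, one-sided alpha = 0.05, paired t-test. Degrees of freedom are 24 and the critical value is 1.711. A true or spurious mean shift of d SDs of the paired difference gives non-centrality d × √25 = 5d, and

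P(reject) = P(T′ > 1.711), with T′ non-central t on 24 degrees of freedom and non-centrality 5d.

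The plan's own figure first: d = 0.60 gives non-centrality 3.0 and a rejection probability of 0.898. The effect detectable with exactly 90% power is 0.603. The plan states no power for its 0.60, but the figure is consistent with about 90% one-sided.

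Now take no true change and an assumed reading shift in the expected direction:

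| Assumed shift (SD) | Share of 0.60 | Non-centrality | P(reject) |
|---|---|---|---|
| 0 | 0 | 0 | 0.050 |
| 0.1 | 1/6 | 0.5 | 0.123 |
| 0.2 | 1/3 | 1.0 | 0.250 |
| 0.3 | 1/2 | 1.5 | 0.426 |

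These rates are per marker. Section 4.1 names eight exhaustion markers, and 10.2.2 states no multiplicity adjustment.

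**The case against.** Several stronger readings are tempting, and the documents do not support them.

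- *The endpoints are read unmasked.* A reader might infer this from the labels. But the labels described are for collection tubes and their bag. What is tested is frozen material whose labels the plan does not describe, and the labelling procedure is only recommended. The supportable statement is that nothing prevents unmasked reading.
- *Every tube shows birth date and initials.* Those are on the bag only.
- *Section 7.2 contradicts 13.4.* The study-number sentence in 13.4 concerns data for analysis and reporting. Record-number tubes going to a laboratory at the same centre can coexist with a coded dataset, so this is a tension. The closer inconsistency is in 13.5, where samples called de-identified carry initials and dates.
- *The laboratory knows who responded.* No section says that laboratory staff open clinical records.
- *The whole immune-restoration claim depends on gating.* Immunoglobulin levels are the other component and are measured by ELISA (4.1), which involves no gating. The responder comparisons are exploratory.
- *The 12%, 25% and 43% rates measure the harm.* They follow from assumed shifts and would hold for any bias of that size in any paired test of 25 patients. The documents give no basis for the size of a shift, or for its existence.

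It is also fair to say that masked reading of correlative assays in an open-label phase II trial is a preference of good practice. These objections stand and limit the point. What they leave is the absence of any coding or masking step for judgement-dependent readings that feed an uncontrolled one-sided test.

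**Conclusion.** The point holds as a minor, inexpensive improvement. Identified and dated specimens reach the laboratory handling the immune testing. Time point can be worked out from record number and date, and no section provides re-coding or masking. The exhaustion readings are therefore open to gating with time point known, in a comparison that has no control arm to absorb a drift.

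The size of any bias is unknown. The calculation shows only that the planned test is sensitive: under the assumption of a 0.1 to 0.3 SD shift, the false-positive rate per marker would be about 12% to 43% in place of 5%, at n = 25. The complete-response primary endpoint and its two-stage rule do not use these samples and are unaffected. The identification rules in 7.2, 13.4 and 13.5 need to be reconciled in any case.

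**What to change.** Leave the clinical identifiers on the collection tubes, where they serve safe patient identification at the blood draw. Then make these changes:

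1. In 7.2, require each plasma and lymphocyte aliquot to receive a coded study number when it is frozen, with no record number, birth date, initials or draw date. Existing trial-office staff hold the key, and the assay reader does not. If the person who processes the tubes also gates the cytometry, the protection is weaker, so the section should name who does each task.
2. In 7.2, state that assays and gating are done blind to time point and response, that all of a patient's time points are run in one batch in random order, and that the code is broken only after the readings are locked.
3. In 13.5, have stored samples carry the same code in place of initials and collection date, consistent with 13.4.

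The samples are already frozen and held before testing, so the coding step fits the existing workflow. The cost is relabelling at freezing, a key log, and a small amount of sample-tracking effort. Sample size, visits and the planned tests do not change.
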